## **8.4. Expected Drop-out Rate**

The expected dropout rate in this study is 30%.

## 8.5. Criterion of Acceptability/Unacceptability of Clinical Trial Result

For the primary efficacy endpoint, a one-sided Wald 97.5% confidence interval for the difference in proportions of subjects with adhesions (INTERCEED™ minus Control) will be constructed and used for testing the null hypothesis of superiority stated in section 8.1. If the upper limit of the confidence interval is smaller than 0, then it will be concluded that INTERCEED™ is superior to Control.

## 8.6. Criteria and Reason for Terminating the Trial based on the Statistical Results

An ad-hoc interim analysis is proposed based on feedback received from the investigators who observed very low rate of adhesions at the second procedure for ostomy reversal.

The conditional power (CP) is the probability that the final result will be significant, given the data obtained up to the time of interim look. The table as below shows the CP per different adhesion rate difference of INTERCEED vs Control arms at the interim look.

Given the assumed 30% drop-out rate, it was planned that a total of 154 participants (77 per arm) with evaluable primary endpoint are available by the study completion. The interim analysis will be performed while at least 94 participants (at least 61% of the total number) have their primary endpoints evaluated in the electronic data collection system. If the CP is  $\leq 60\%$ , the observed adhesion rate difference magnitude between two arms is only around 0.10, which is much less than the assumed difference magnitude of 0.25 used for sample size calculation. Therefore, the study will be terminated due to low adhesion rate and small effect size between INTERCEED and control arms. Otherwise, the study will continue until the study completion as planned.

There is a database lock for this interim analysis. All data for the analysis will be cleaned with 100% source data validation. The statistical analysis will be conducted per updated and approved protocol and SAP to determine if the interim results meet the pre-specified threshold of early discontinuation ( $CP \leq 60\%$ ).

Table: Conditional power per different treatment effect size observed at interim look

Observed adhesion difference between INTERCEED vs control at interim look	Data availability at interim look				
	Percentage of participants with evaluable primary endpoint (number of participants)				
	61% (94)	66% (102)	70% (108)	72% (112)	75% (116)
-0.02	0.19	0.11	0.07	0.04	0.02
-0.06	0.35	0.26	0.2	0.16	0.12
-0.08	0.45	0.37	0.3	0.26	0.21
-0.1	0.55	0.48	0.42	0.38	0.34
-0.11	0.59	0.54	0.49	0.45	0.41
-0.12	0.64	0.6	0.56	0.52	0.49
-0.13	0.69	0.65	0.62	0.6	0.57
-0.14	0.73	0.7	0.68	0.66	0.64
-0.15	0.77	0.75	0.74	0.72	0.71

-0.16	0.81	0.8	0.79	0.78	0.78
-0.18	0.87	0.87	0.87	0.87	0.87

## **8.7. Statistical Method of All Data, together with the Handling Method of Missing, Unused and Error Data (including Termination and Withdrawal Halfway) and Unreasonable Data**

All study endpoints will be analyzed using the available data. There will be no missing data imputation in this study.

## **8.8. Reporting Procedure of Deviation from Original Statistical Plan**

Any changes from the original planned statistical analyses will be specified in the protocol revisions, if applicable, and/or in a final or amended statistical analysis plan.

The statistical analysis plan will be updated accordingly per the ad-hoc interim analysis.

## **8.9. Selection Criteria and Reason of Subjects Included in the Analysis**

All subjects that meet the inclusion/exclusion criteria are considered to meet the requirements for recruitment.

The following three analysis sets are defined in this study:

- The Intent-to-Treat (ITT) set will contain all randomized subjects.
- The Per-Protocol (PP) set will contain all subjects in the ITT set who have no major protocol deviations.
- The Safety set will contain all subjects who receive study device.

Major protocol deviations are deviations that have an impact on the primary endpoint, or that have an impact on the randomization assignment. These will be determined prior to database lock.

The primary effectiveness endpoint will be analyzed using the ITT and the PP set. However, the primary analysis will be based on the ITT set. The PP analysis will be considered supportive.

In all cases, treatment allocation will be based on randomization for the primary effectiveness endpoint using the ITT. If more than 11 subjects are mis-randomized, then an additional confirmatory analysis based on treatment received will be performed for the primary effectiveness endpoint, using the ITT.

The secondary effectiveness endpoint will be analyzed using the ITT set, while the safety endpoints will be analyzed using the Safety set.

## **9. Data management**

The individual subject data collected during the period of this trial will be recorded in the corresponding database. The data is audited by the data management group after collecting the data. Any unexpected or missing data points will generate inquiry and the unexpected or missing data will be forwarded to the site for solving it. When all subjects have the opportunity to complete

all follow-up evaluation, this study will be closed and the data analysis will be performed.

## 10. FEASIBILITY ANALYSIS

### 10.1. Likelihood Analysis of Success

INTERCEED™ was first marketed in America in 1989, which was used in gynecological pelvic surgery to prevent the occurrence of postoperative adhesion. It was approved in Europe in 2002 to be used in abdominal operation. It was introduced in the Chinese market in 2004 and approved to be used in gynecological pelvic surgery. It has been widely used at home and abroad for nearly 30 years.

INTERCEED™ is a sterile, single-use-only, absorbable off-white knitted fabric prepared by the controlled oxidation of regenerated cellulose. INTERCEED™ reduces the formation of adhesions by physically separating the surfaces of tissues that are adjacent to each other during the reperitonealization phase.

The currently existing clinical literatures regarding the study product showed that INTERCEED™ could reduce the occurrence of postoperative adhesion when compared to the blank control [6,7,11-19]. Especially the two papers (e.g. Sekiba and Azziz) [13,14] studying the tissue, pelvic wall similar to abdominal wall clearly pointed out that the incidence of adhesions in pelvic wall was about 76% when INTERCEED™ was not used, while the incidence of adhesions was reduced to 40%-50% when INTERCEED™ was used. It can be seen that INTERCEED™ has a prominent impact on preventing the occurrence of adhesions [11,12].

### 10.2. Likelihood Analysis of Failure

Although a large amount of clinical literature showed that INTERCEED™ could reduce the occurrence of postoperative adhesion when compared to the blank control, most of these studies were limited to uterus and ovary, no clinical literatures related to the application in abdominal cavity or abdominal wall.

An ad-hoc interim analysis is proposed based on feedback received from the investigators who observed very low rate of adhesions at the second procedure for ostomy reversal. The ad-hoc interim analysis is planned to reevaluate the study assumptions used for hypothesis testing. If the assumptions don't hold, the likelihood analysis of failure may increase to be moderate.

## 11. QUALITY CONTROL OF CLINICAL TRIAL

During the clinical study, the sponsor and investigator should execute their respective responsibilities according to the Good Clinical Practice for Medical Device Trials and applicable related Chinese and international regulations. They should also strictly follow the clinical trial protocol in order to ensure the quality of clinical trial.

The sponsor should organize the training on clinical trial protocol and the use and maintenance of investigational medical device for all investigators participating in the trial, so as to ensure the consistency in the implementation of clinical trial protocol, the use of investigational medical device.

During the implementation of study, the sponsor is responsible for monitoring each phase of clinical trial. The clinical monitor employed by the sponsor or appointed representative should comply with the related standard operating procedure (SOP) and clinical trial protocol that are

established by the sponsor to monitor the clinical trial, so as to ensure the complete, accurate, true and reliable data.

To ensure the quality of study, the sponsor may authorize the eligible QA auditor to audit the clinical trial as needed. The investigator should allow the auditors to look up the original data and documents related to this study after receiving the notification.

When the food and drug regulatory authority, competent department of health and family planning or other regulatory agencies send the inspection personnel to carry out the inspection, the clinical trial institution and investigator should cooperate and immediately notify the sponsor.

## **12. CLINICAL TRIAL-INVOLVED ETHICAL ISSUES AND INFORMED CONSENT**

### **12.1. Ethical Concerns**

In the whole study process, the study protocol (and update), informed consent form (and update) and other applicable documents related to the study must be submitted to the relevant Ethics Committee and can't be implemented until the written approval is obtained.

Before the subjects participate in the clinical trial, the investigator must fully explain this study and answer all questions raised by subjects. Each subject (or legally authorized representative) must voluntarily sign and date the informed consent form (and other documents as per local regulations) that is approved by the Ethics Committee prior to implementing any study-related operations. The process of obtaining the informed consent needs to be clearly documented in the original record of the subject. The subject may request to withdraw the informed consent at any time in the study process. This withdrawal will not affect the subsequent therapy of the investigator for the subject.

The production of investigational product should meet the relevant requirements of applicable quality management system for medical devices; the processing and storage of investigational product should meet the requirements of specifications and related standard operating procedure; the investigational product should be used according to the approved protocol and related operation instructions.

The collection, use and disclosure of all personal data (including the patient health and medical information) should comply with the applicable laws and regulations with regard to the personal data protection and security. When collecting and processing such personal data, appropriate measures are to be taken to maintain the confidentiality of patient health and medical information and to prevent access by unauthorized persons.

### **12.2. Approval of Trial Protocol**

The trial protocol should be internally approved and filed according to the company's standard operating procedure (SOP) prior to submitting to the external agency (including but not limited to the government regulatory agencies, Ethics Committee).

The clinical trial protocol should not be implemented until the written approval is obtained from the Ethics Committee according to the relevant requirements of laws and regulations.

### **12.3. Process of Informed Consent and Text of Informed Consent Form**

#### **12.3.1. Process of Informed Consent**

The informed consent of all potential subjects must be obtained prior to performing any study operations/procedures. Once the investigator determines that the patients are suitable for participating in this study, the investigator must explain the background of the study presented and the benefits and risks of surgery and study to the patients and answer the questions raised by patients. Only the patient who signs the informed consent form that is approved by the Ethics Committee (EC) prior to participating in the study is eligible to participate in this study. The patient who doesn't sign the written informed consent form is not eligible to participate in this study.

Each subject (or legally authorized representative) must sign and date the informed consent form that is approved by the (EC) (and other documents as per local regulations) prior to implementing any study-related items or operations not belonging to the standard treatment and after the nature of this study is fully clarified.

The process of obtaining the written informed consent needs to prove that the subjects volunteer to participate in this study. All aspects of this study must be clarified to the subjects prior to signing the informed consent form. The process of obtaining the informed consent must be clearly documented by the investigator and/or designated person in the original clinical trial documents of subjects. The investigator has responsibilities to ensure the process of obtaining the informed consent is implemented according to the Good Clinical Practice for Medical Device Trials and related regulations, such as ISO 14155, the Declaration of Helsinki.

#### **12.3.2. Text of Informed Consent Form**

See the Informed Consent Form attached to the protocol.

### **13. REGULATIONS OF ADVERSE EVENT AND DEVICE DEFECT REPORTING**

#### **13.1. Adverse event**

An AE is defined as any untoward medical occurrence in the process of clinical trial, regardless of its relationship to the investigational medical device.

The investigator should determine whether an AE occurs and determine its relationship to the study device or surgery at each evaluation for the subjects recruited for the clinical study.

All AEs, study device faults and other product problems must be recorded in the medical record and entered in the CRF. All AEs need to be recorded in the EDC system in 2 weeks.

Postoperative pain, fever and laboratory abnormalities is expected and will not be documented as an adverse event unless the Investigator considers the pain or fever to exceed that normally anticipated following the surgery or related to study devices. Also, the adverse event, not including the serious adverse event and ileus event, which is "not relative" or "unlikely related" to the study device and occurred 1. between 30 days after Phase 1 operation and the hospitalization for Phase 2 operation or 2. between Visit 6 and Visit 7 should not be documented.

The severity of adverse event is graded into the following levels:

**Mild:** Existing signs or symptoms have no impact on the usual activities of the subjects, or transient, no treatment required, with no sequel.

**Moderate:** Have an impact on the usual activities of the subjects, with no interference, with possible need of treatment.

**Severe:** Cause the symptom of severe discomfort, resulting in major impact on the usual activities of the subjects, medical intervention or treatment required.

The causal relationship of adverse events should be determined as follows:

**Not related:** The event is definitely not related to the use of product

**Unlikely related:** The time sequence between the use of product and the event shows that the event is unlikely associated,

**Possibly related:** The time sequence between the use of product and the event shows that the event is likely associated, or AE may also be caused by the disease or concomitant treatment of the subjects,

**Probably related:** The time sequence shows the event has temporal relationship to the use of investigational product, or the event is alleviated at the end of use of product, or it is unable to give reasonable explanation to this event according to the disease of the patient,

**Definitely related:** The time sequence shows the event has temporal relationship to the use of investigational product, or the event is alleviated after the withdrawal of product, or the event occurs again when the product is reused (reactivated).

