#### **7.1.7. Safety Evaluation Method**

##### **1) Description of safety parameters**

The safety parameters in this study are the incidence of surgical site infections, wound dehiscence, delayed wound healing, any adverse events and defects of study product.

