### **13.4. Reporting Procedure, Contact Information**

The investigator should ensure to provide the sufficient treatment for Any adverse event of any

subjects, including the laboratory detection value with clinical significance and related to this study.

The adverse event is reported from the start of signing the informed consent to the end of the study of subjects. All adverse events should be followed up, until the adverse event is resolved, stable or the study is completed.

The investigator should record the nature, severity, treatment and outcome of serious adverse event, and determine whether it is related to the study device, drug administration or surgery specified in the study protocol. The investigator will report the adverse event to the sponsor via the Case Report Form (CRF).

The investigator must submit the serious adverse events occurred in the study and the device defects that may cause serious adverse event to the sponsor and the regulatory authorities at every level (or designated person) immediately after being informed of the event; if required by the sponsor, the further information should be provided.

All serious adverse events need to be followed up until the event is resolved (with or without sequela). When the event is not resolved or stable at the end of study, the medical monitor in this clinical study will decide whether it is necessary to collect the further follow-up information.

The investigator and sponsor should report the serious adverse events occurred in the study and the device defects that may cause serious adverse event to the regulatory authorities at every level according to the requirements of laws and regulations.

The study device with device defect should be returned to the sponsor according to the instructions given in Section 13.3 of this study. Once a device defect is found, the site should inform the sponsor as soon as possible, and report the device related information on the relevant CRF.

The contact person to report adverse event and device defect is as follows:

Adverse event: [contact]

Device defect: [contact]

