3.4.1 Adverse events

All adverse events (AEs) will be summarized, and the AEs will be coded using the MedDRA 23.1 dictionary.

An adverse event refers to any detrimental medical events in the course of a clinical trial, whether or not related to the investigational medical device. All AEs, study device failure, and other product problems must be documented in the medical record since the signing of informed consent. In the meantime, for non-serious AEs (excluding ileus-related events) that occur during the period from 30 days after the phase 1 operation to the second hospital admission before the phase 2 operation specified in the protocol, or between Visit 6 and Visit 7, recording and collection are not required if they are assessed as not related or unlikely related to the study device by the study doctor.

The incidences of AEs will be summarized per treatment group and in total using the number of cases (percentage). During the summary of number of cases per PT, if a subject experienced the same AE (distinguished per PT) repeatedly, he/she will be counted once only when calculating the number of cases; During the summary per severity of AE, for the same AE of different severity, the most severe one will be counted when calculating the number of cases.

According to the rules above, the AEs will be summarized generally and per SOC and PT level, and the types of AEs are summarized as follows:

- All AEs recorded during the study period in the EDC
- AEs related to the study product/phase 1 operation/phase 2 operation (including: definitely related, probably related, possibly related, and unlikely related)
- SAE
- Serious AEs related to the study product/phase 1 operation/phase 2 operation (including: definitely related, probably related, possibly related, and unlikely related)

In addition, for AEs that have occurred at least once, the number of cases and percentage will be calculated per SOC, PT, and severity (mild, moderate, and severe), and the same analysis will also be performed for AEs related to the study product.

All AEs will be tabulated to record the AE name (PT), onset date, end date, severity of AE, SAE or not, classification of SAE, relevance with the study product, action taken, and outcome, etc., and the AEs/SAEs leading to death will be tabulated independently.

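### Protocol 13.1 excludes post-operative laboratory abnormalities from AE recording without the exception it gives to pain and fever, and this conflicts with 13.4

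*Protocol*

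**What the plan says.** Protocol 13.1 starts from a wide definition: "An AE is defined as any untoward medical occurrence in the process of clinical trial, regardless of its relationship to the investigational medical device". It adds a general duty: "All AEs, study device faults and other product problems must be recorded in the medical record and entered in the CRF". It then narrows this: "Postoperative pain, fever and laboratory abnormalities is expected and will not be documented as an adverse event", with the exception "unless the Investigator considers the pain or fever to exceed that normally anticipated following the surgery or related to study devices".

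The next sentence of 13.1 sets a time-window rule. Events that are neither serious nor ileus, and are judged not or unlikely related to the device, are left undocumented in two periods: from 30 days after the Phase 1 operation to the Phase 2 hospitalization, and between Visit 6 and Visit 7.

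Protocol 13.4, in a sentence about providing treatment for adverse events, describes those events as "including the laboratory detection value with clinical significance and related to this study". It also keeps a separate duty for serious events: "The investigator should record the nature, severity, treatment and outcome of serious adverse event".

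SAP 3.4.1 says "All AEs, study device failure, and other product problems must be documented in the medical record since the signing of informed consent". It repeats the time-window rule but not the exclusion of pain, fever and laboratory abnormalities.

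The safety parameters in Protocol 7.1.7 are surgical site infection, wound dehiscence, "delayed wound healing, any adverse events and defects of study product". No laboratory parameter is listed.

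**The concern.** The exclusion covers three kinds of event and the exception covers two. An unusually severe fever is recorded. An unusually large laboratory change is not, unless it is judged device-related, and even that route is unclear. Section 13.4 points the other way, so two sites could each follow the protocol in good faith and record different events.

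Safety is part of the primary objective, and the AE tables are where a laboratory finding would have to appear. At stake is the completeness of those tables, and whether the recording rule works the same way in the two arms.

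**Working it through.** No sample size, rate or error level enters this point, so there is no figure to reproduce. The check sets the passages side by side.

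1. **The exception in 13.1.** Its subject is pain or fever. Read strictly, the device-relatedness limb attaches to the same subject, so even a device-related laboratory abnormality is not clearly brought back. On the more generous reading, device-relatedness is the one route back in. On neither reading does size or clinical significance count.

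2. **The counter-passage in 13.4.** It counts laboratory values that are clinically significant and related to the study among adverse events. Study-related is wider than device-related: an abnormality caused by the operation could qualify. However, the sentence is about treating the subject and does not expressly override 13.1.

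3. **Outcome by type of post-operative event.**

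| Event | 13.1 read literally | Other passages | Result |
|---|---|---|---|
| Pain or fever, beyond expectation or device-related | Back in | None needed | Recorded |
| Serious event with a laboratory component | Not the governing text | 13.2 and 13.4 cover serious events | Recorded |
| Diagnosed infection | An illness, not a laboratory abnormality | SSI is collected at Visits 4 to 7 | Recordable as AE (subject to the windows) or SSI |
| Non-serious laboratory abnormality, device-related | Unclear | 13.4 counts it if clinically significant | Ambiguous |
| Non-serious, clinically significant, study-related but not device-related | Excluded | 13.4 counts it | Contradiction |
| Non-serious, beyond expectation, not study-related | Excluded | Nothing brings it back | Not recorded |

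4. **When the exclusion adds anything.** Within the two windows of the time-window rule, unrelated non-serious events other than ileus already go undocumented, so the laboratory clause removes little more there. Its added effect falls mainly in the 30 or so days after Phase 1 and from the Phase 2 admission to Visit 6. Abnormalities before Phase 1 are not post-operative and are untouched.

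5. **Other routes into the report.** The visit schedule lists no laboratory test except the pregnancy test. SAP 3.4 plans no laboratory analysis. A laboratory finding without a diagnosis can reach the report only as an AE.

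6. **Symmetry between arms.** Controls receive no barrier, so device-relatedness has no natural application to them, and Protocol 7.1.4 states that the implanting surgeon cannot be blinded. On the generous reading of the exception, the same abnormality could be recorded in an INTERCEED subject and not in a control.

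**The case against.** The strongest reply is that leaving out expected post-operative laboratory changes was deliberate. The Revision Record shows the rule entering with version 3.0, and a specific exclusion may properly qualify a general AE definition. That stands as a reason to keep an exclusion. It does not explain why unexpected pain and fever return and unexpected laboratory changes do not, nor does it settle the conflict with 13.4.

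Four stronger readings are tempting, and the documents do not support them.

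- *Such abnormalities are never recorded.* Section 13.4 counts the clinically significant, study-related ones among adverse events. For those the protocol contradicts itself rather than clearly excluding them.
- *The loss runs from Phase 1 to the end of the study*, because 13.1 puts no end date on the post-operative period. The time-window rule already leaves most such events undocumented over much of that time.
- *Intra-abdominal infections would vanish from the tables because the markers that signal them are excluded.* The clause excludes a laboratory abnormality, not the illness behind it. A diagnosed infection remains recordable as an AE, and the protocol separately collects surgical site infections.
- *The SAP presents incomplete tables as complete.* The table listed in SAP 3.4.1 is limited to AEs recorded in the EDC during the study. The SAP is silent on the exclusion, which is an omission of detail and not a rival rule.

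**Conclusion.** The point holds in a narrow form. Section 13.1 gives laboratory abnormalities no exception for exceeding expectation or for clinical significance, and it conflicts with 13.4. Followed literally, isolated, non-serious laboratory abnormalities beyond what the surgery explains, with no separately recorded diagnosis, can be missing from the AE tables. The loss is mainly perioperative, and at best the only way back in under 13.1 is one that controls cannot use.

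The size cannot be given, because the documents state no rate. A reader might apply an assumed rate to the 110 subjects per arm: 5%, 10% and 20% give 110 × 0.05 = 5.5, 110 × 0.10 = 11 and 110 × 0.20 = 22. These figures should not be used as an estimate. The rates have no source in the documents, and the calculation takes no account of the windows or of abnormalities for which a diagnosis is recorded.

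The conclusion assumes that sites apply 13.1 as written and that the separate duty for serious events in 13.2 and 13.4 prevails over the exclusion. Nothing here touches the primary endpoint, power or significance level.

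**What to change.** Reconcile 13.1 with 13.4 by widening the exception, for example: *unless the investigator considers the pain, fever or laboratory abnormality to go beyond what the surgery would normally produce, or the laboratory abnormality to be clinically significant, judged the same way in both arms, or any of the three to be related to the study device*. Clinical significance is a test that 13.4 already uses. The sponsor should also say whether relation to the study, which 13.4 adds, is required.

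State the same recording rule in SAP 3.4.1, next to the time-window rule already there, so that readers of the AE tables know what they leave out.

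The cost is one sentence in each document and a few more AE entries, with no new tests. The change leaves the time-window rule in place and would not recover events excluded by it.
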